### **6.2 Dose modifications**

#### **6.2.1 Dose modification and dose delay**

For patients who do not tolerate the protocol-specified dosing schedule, dose adjustments are permitted in order to allow the patient to continue the study treatment. Details of study treatment dose levels are provided in Table 6-1.

**Table 6-1a      Everolimus dose levels**

Dose level	Dose and schedule
0 (starting dose)	10 mg daily
-1	5 mg daily
-2	2.5 mg daily

**Table 6-1b      Temozolomide dose levels**

Dose level	Dose and schedule
+1 (dose increased at cycle 2 at treating MD's discretion)	200 mg/m  /day for days 1-5 of each 28-day cycle
0 (starting dose)	150 mg/m  /day for days 1-5 of each 28-day cycle
-1	100 mg/m  /day for days 1-5 of each 28-day cycle
-2	75 mg/m  /day for days 1-5 of each 28-day cycle

If a patient has already decreased 2 dose levels of a specific drug, no further dose reduction is permitted. Patients who need an additional dose reduction will be required to discontinue the drug in question.

In the combination treatment arm, hematologic toxicity will initially be presumed due to temozolomide. Nausea, emesis and constipation during or within a few days after temozolomide dosing will be presumed due to temozolomide. Acneiform rash will be presumed due to everolimus; all other rash will initially be presumed due to temozolomide. Elevation of liver enzymes, hyperglycemia, hyperlipidemia, mucositis, diarrhea, and noninfectious pneumonitis will initially be presumed due to everolimus.

Treatment or visit delays for public holidays or weather conditions do not constitute a protocol violation.

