#### **4 Study design**

Treatment for patients with previously untreated LGG will be selected by whether or not their tumor has ATRX loss and/or 1p/19q chromosomal co-deletion. If the tumor is ATRX lost or 1p/19q intact, then patients will be further selected by whether or not their tumor demonstrates activation of the PI3K/mTOR pathway. If activation is present, patients will be treated in Arm 1 with single-agent everolimus at 10 mg daily continuously. If activation is not present, patients will be treated in Arm 2 with combined everolimus and TMZ. Everolimus will be given at 10 mg daily continuously, and TMZ will be dosed initially at 150 mg/m^2/day for 5 days out of a 28-day cycle. If ATRX is intact, 1p/19q co-deletion should be confirmed, or if only 1p/19q co-deletion is available and present, patients will be treated in Arm 3 with single-agent everolimus at 10 mg daily continuously. In all arms, treatment with everolimus will continue for up to 24 cycles, after which patients will be followed with interval MRIs until progression. In Arm 2, TMZ will be stopped after 12 cycles.

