#### **6.1.5 Temozolomide dosing regimen**

Temozolomide will be orally self-administered at approximately the same time each day on days 1 through 5 of each 28 day dosing cycle. A temozolomide dose of 150 mg/m^2 per day will be given for Cycle 1 of TMZ. This dose may increase to 200 mg/m^2 body surface area per day in subsequent TMZ cycles per the treating physician's discretion. Any change in weight of more than 10% will require re-calculation of the administered temozolomide dose; otherwise, dosing may be based on the baseline weight. The total dose of TMZ shall be rounded to the nearest 5 mg. Dosing should occur according to instructions in the product label and per standard clinical practice.

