**Table 6-3 Dosing guidelines for everolimus-related hematologic toxicities**

Toxicity	Action
Grade 2 thrombocytopenia (platelets $<$ 75, $\geq$ 50x10  /L)	No action

Grade 3 thrombocytopenia (platelets <50, $\geq 25 \times 10^9/L$ )	Interrupt everolimus until resolution to grade $\leq 1$ If resolution occurs $\leq 7$ days, reintroduce everolimus at the dose level prior to interruption. If resolution occurs $> 7$ days and $\leq 28$ days, reintroduce everolimus at one dose level lower, if available.
Grade 4 thrombocytopenia (platelets < 25 $\times 10^9/L$ )	Interrupt everolimus until recovery to grade $\leq 1$ . Then reintroduce everolimus at one dose level lower, if available.
Grade 3 neutropenia or anemia (neutrophil <1, $\geq 0.5 \times 10^9/L$ )	Interrupt everolimus until resolution to grade $\leq 1$ or baseline value If AE resolution occurs $\leq 7$ days, reintroduce everolimus at the same dose level. If AE resolution occurs $> 7$ days and $\leq 28$ days, reintroduce everolimus at one dose level lower, if available.
Grade 4 neutropenia or anemia	Interrupt everolimus until recovery to grade $\leq 1$ or baseline value. Reintroduce everolimus at one dose level lower, if available.*
Febrile neutropenia	Interrupt everolimus until resolution to grade $\leq 1$ (or baseline value) and no fever. Reintroduce everolimus at one dose level lower, if available.*
Recurrence of grade 3 toxicity after dose reduction	Reduce dose to the next lower dose level, if available. The lowest possible dose level of everolimus is 5 mg every other day (2.5 mg daily). Below this level, everolimus must be discontinued.
*Recurrence of grade 4 toxicity (including febrile neutropenia) after dose reduction	Discontinue everolimus
*Any hematologic toxicity requiring Everolimus interruption for > 28 days	Discontinue everolimus

Overall, safety data available from completed, controlled and uncontrolled studies indicate that everolimus is generally well tolerated at weekly or daily dose schedules. The safety profile is characterized by manageable adverse events (AEs). These AEs are generally reversible and non-cumulative.

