### 6.2.3 Management of specific temozolomide toxicities

Temozolomide will be administered every 4 weeks, unless the patient has not recovered from treatment-related adverse events associated with a prior course. Recovery has occurred once all of the following conditions have been met:

- ANC  $\geq 1500/\mu\text{L}$ ;
- Platelet count  $\geq 100,000/\mu\text{L}$ ;
- All drug-associated non-hematological toxicities have recovered to  $\leq$  grade 2 or to baseline levels and the investigator does not feel that any of these toxicities present any hazard to patient safety or care.

If recovery has not occurred by Day 28, the subsequent course of treatment will be delayed until these criteria have been met. The dose of temozolomide in subsequent courses will be individually titrated (see Table 6-7 below). Growth factors cannot be used to induce elevations in neutrophil count for the purposes of administration of temozolomide on the scheduled dosing or to allow treatment with temozolomide at a higher dose.

**Hematological Criteria:** If temozolomide cannot be administered on the scheduled day of dosing, the CBC will be repeated weekly for up to and including 4 weeks until the ANC is  $\geq 1500/\mu\text{L}$  and platelet count is  $\geq 100,000/\mu\text{L}$ . If these hematological criteria are met, chemotherapy may be administered according to the dose adjustments outlined in Table 6-5 below. If the ANC remains  $< 1500/\mu\text{L}$  or platelet count is  $< 100,000/\mu\text{L}$  at 4 weeks, the decision to restart must be reviewed with the study chair or their designated alternate before proceeding. No more than two dose reductions will be allowed.

The dose of temozolomide administered for subsequent cycles will be determined according to the nadir ANC and nadir platelet count of the immediately previous cycle for temozolomide (see Table 6-7).

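### In Arm 2, no rule requires holding everolimus for grade 4 cytopenia or febrile neutropenia while the event is presumed due to temozolomide

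*Combined protocol and SAP*

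**What the plan says.** - **Attribution.** Section 6.2.1, below Table 6-1b: "In the combination treatment arm, hematologic toxicity will initially be presumed due to temozolomide". It gives no grade limit, no criterion for re-attribution and no end date.
- **Everolimus rules.** Table 6-3 is titled "Dosing guidelines for everolimus-related hematologic toxicities", and Section 6.2.2 introduces it with the same scope. It interrupts everolimus for grade 4 thrombocytopenia, for grade 4 neutropenia or anemia, and for febrile neutropenia. In each case everolimus restarts one level lower. The febrile neutropenia row holds everolimus to grade 1 or less "or baseline value) and no fever. Reintroduce everolimus at one dose level lower, if available". A separate row, "Any hematologic toxicity requiring Everolimus interruption for" more than 28 days, ends everolimus.
- **Temozolomide rules.** Section 6.2.3: "The dose of temozolomide administered for subsequent cycles will be determined according to the nadir ANC and nadir platelet count" of the cycle just completed. On delay: "If recovery has not occurred by Day 28, the subsequent course of treatment will be delayed until these criteria have been met". Table 6-7 lowers the next temozolomide dose at nadir levels 3 and 4. Neither the section nor the table instructs a hold of everolimus.
- **Schedules.** Section 4 on Arm 2: "Everolimus will be given at 10 mg daily continuously". Section 6.1.5: temozolomide is taken "on days 1 through 5 of each 28 day dosing cycle". Section 7.1.2 sets Arm 2 blood counts at Day 21 and Day 28 (each plus or minus 3 days) from the first temozolomide dose.

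**The concern.** Attribution decides which table applies, and the two tables act on different drugs at different times. For a patient in Arm 2 with a grade 4 count or febrile neutropenia, the presumption leads to rules about the next temozolomide course, although temozolomide dosing for the current cycle is already over. The drug still being swallowed each day is everolimus, which Section 6.2.2.1 describes as immunosuppressive. The protocol's own judgement in Table 6-3 is that everolimus should stop for such events when it is held responsible. In the arm with the added myelosuppressive drug, that stop becomes discretionary for as long as the first attribution stands.

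**Working it through.** **1. Do the two tables describe the same events?** Since 1 x 10^9/L = 1,000/µL:
- Platelets below 25 x 10^9/L (Table 6-3, grade 4) = below 25,000/µL (Table 6-7, level 4).
- Table 6-3 puts grade 3 neutropenia at 0.5 to below 1 x 10^9/L = 500 to 999/µL (Table 6-7, level 3). Grade 4 is therefore below 500/µL (level 4).

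For platelets and neutrophils the events are identical.

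**2. What does each route require?**

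| Event | Judged everolimus-related (Table 6-3) | Presumed due to temozolomide (6.2.3, Table 6-7) |
|---|---|---|
| Grade 4 thrombocytopenia | Interrupt everolimus | Lower the next temozolomide dose; delay the course if not recovered |
| Grade 4 neutropenia | Interrupt everolimus | Same |
| Febrile neutropenia | Interrupt everolimus | Not named; reached only through the neutrophil nadir |
| Grade 4 anemia | Interrupt everolimus | No row; hemoglobin is absent from the recovery conditions |

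On the right-hand route, anemia is reached only by the rule that stops temozolomide when a toxicity of grade 3 or worse follows two reductions. That rule then allows everolimus to go on.

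**3. Timing.** The last temozolomide dose is on Day 5 and the nadir count is at Day 21. The first point at which 6.2.3 acts is Day 28.
- Daily everolimus doses in between: 28 - 21 = 7.
- Count taken at Day 18: 28 - 18 = 10. At Day 24: 28 - 24 = 4.

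This is the time until the temozolomide rules first act. It is not the number of doses that Table 6-3 would have withheld, because that hold runs to recovery and may be shorter or longer. If temozolomide is then delayed, 6.2.3 repeats the count weekly for up to 4 weeks, still with no everolimus instruction. Section 7.1.2 keeps the 28-day cycle fixed despite such delays, so a temozolomide delay does not itself pause everolimus.

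**4. Does another rule require a hold?**
- The opening of 6.2.1 permits dose adjustments for intolerance but requires none.
- The catch-all grade 4 row is in Table 6-2, which covers non-hematologic everolimus-related toxicity.
- Section 6.2.2.1 asks the physician to consider interruption once an infection is diagnosed, and requires discontinuation only for invasive systemic fungal infection. Fever with neutropenia but no diagnosed infection is not reached.
- The Site Committee reviews in Section 8.4 and Appendix 3 help detect events but supply no dosing rule.

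**5. How often?** Section 2.4 describes myelosuppression as mild at the phase I recommended dose, with 2 patients each having grade 3 thrombocytopenia, lymphopenia and granulocytopenia. In the melanoma study, 9 of 48 patients (9/48 = 18.75%) had a dose reduction for myelotoxicity, on a different schedule. Neither figure is a rate of grade 4 or febrile events, so no expected number for the 35 Arm 2 patients can be derived.

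**The case against.** The strongest reply is that this argues from silence. The presumption is only an initial one, Table 6-3 is not restricted by arm, and dose adjustments are allowed. A competent physician facing a grade 4 count would probably hold everolimus. This much stands: the protocol nowhere orders everolimus to continue. A reader might infer that it does, or that Table 6-3 is switched off in Arm 2, and the text supports neither. What remains is that a hold depends on individual judgement, with no criterion for when to re-attribute.

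A reader might also infer that Arm 2 is less protected overall. The documents do not support that. Arm 2 has an additional Day 21 count, a narrower Day 28 window while on both drugs, weekly counts during a temozolomide delay, and study-chair review of restarting if counts have not recovered at 4 weeks. These measures improve detection and govern temozolomide, but they do not supply the missing everolimus instruction.

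Infection is partly covered, since a serious infection judged everolimus-related can fall under Table 6-2. Neutropenic fever without a diagnosed infection cannot.

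Finally, Table 6-3 also interrupts everolimus for grade 3 thrombocytopenia, neutropenia and anemia, so a cut at grade 4 leaves part of the mismatch in place. That is true. The cut is a choice to act where the hazard is greatest and to leave grade 3 events to the attribution rule.

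**Conclusion.** The gap is real but limited. While a grade 4 cytopenia or febrile neutropenia in Arm 2 is presumed due to temozolomide, no rule requires everolimus to be held, although Table 6-3 interrupts it for the same event when everolimus is held responsible. At a Day 21 nadir, about 7 daily doses (4 to 10) precede the first action under the temozolomide rules. This rests on the stated schedules and on the event being found at that count.

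It would be tempting to go further and say how many patients would be exposed or harmed. The documents give no grade 4 or febrile event rate for the combination, so the size of the risk is unknown. The lack of a stated end to the presumption once temozolomide is finished is only a point to clarify. The change is worth making because it is cheap and makes a safety action explicit, not because a large risk has been shown.

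**What to change.** After the presumption sentence in 6.2.1, add:

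> In Arm 2, for grade 4 thrombocytopenia, neutropenia or anemia and for febrile neutropenia, everolimus is interrupted until the Table 6-3 recovery criterion is met, regardless of attribution; if the event remains attributed to temozolomide, everolimus resumes at the same dose.

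Add one row to Table 6-7:

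> Grade 4 anemia: hold temozolomide until grade 1 or less or baseline, then decrease one dose level.

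Leave the 28-day discontinuation rule in Table 6-3 as it is. If the sponsor also wants to state when the presumption ends, define it as 28 days from the first dose of the last temozolomide course actually given. That leaves 28 - 5 = 23 days after the final dose. Tying it to the study cycle would misfire, because under 7.1.2 Day 1 does not move with a temozolomide delay. A last course started two weeks late would be taken on cycle days 15 to 19, leaving only 28 - 19 = 9 days.

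The cost is one sentence and one table row, with no new visits, tests or patients. The downside is some lost everolimus doses in Arm 2. A hold longer than 28 days would end everolimus and could count toward the discontinuation rate monitored under Section 9.4. Restarting at the same dose limits the loss when temozolomide is responsible.

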### **6.2.2      Management of specific everolimus toxicities**

[Table 6-2](#) and [Table 6-3](#) list the dosing guidelines for everolimus-related non-hematologic and hematologic toxicities.

**Table 6-2 Dosing guidelines for Everolimus-related non-hematologic toxicities**

Toxicity	Action
Non-Infectious Pneumonitis	Please refer to Table 6-6 .
AST or ALT elevation Grade 1 (> ULN - 3.0 x ULN) Grade 2 (> 3.0 - 5.0 x ULN)	Maintain current dose level
AST or ALT elevation Grade 3 (> 5.0 - 20.0 ULN)*	Interrupt everolimus administration until resolution to $\leq$ grade 1 (or $\leq$ grade 2 if baseline values were within the range of grade 2). If resolution occurs $\leq$ 7 days, everolimus should be re-started at the dose level prior to interruption. If resolution takes $>$ 7 days, or if event recurs within 28 days, hold everolimus until recovery to $\leq$ grade 1 or baseline grade / value and reintroduce everolimus at one dose level lower, if available.
AST or ALT elevation Grade 4 (> 20 x ULN)*	Interrupt everolimus administration until resolution to $\leq$ grade 1 (or $\leq$ grade 2 if baseline values were within the range of grade 2). If resolution occurs $\leq$ 7 days, everolimus should be re-started at one dose level lower. If resolution takes $>$ 7 days, discontinue everolimus. Discontinue everolimus.
Recurrence of grade 4 after dose reduction or toxicity requiring Everolimus interruption for $>$ 28 days	
Intolerable grade 2 mucositis, or grade 3 AE, except hyperglycemia or hypertriglyceridemia or hypercholesterolemia (see Section 6.2.2.5 )	Interrupt everolimus administration until resolution to $\leq$ grade 1 or baseline grade / value. If resolution occurs within $\leq$ 7 days, everolimus should be re-started at the dose level prior to interruption. If resolution takes $>$ 7 days, or if event recurs within 28 days, hold everolimus until recovery to $\leq$ grade 1 or baseline grade / value and reintroduce everolimus at one dose level lower, if available. Patients will be withdrawn from the study if they fail to recover to $\leq$ grade 1 or baseline grade / value within 28 days.
Any other grade 4	Hold everolimus until recovery to grade $\leq$ 1 or baseline value Reintroduce everolimus at one dose level lower, if available.
Grade 3 or 4 clinical liver failure (asterixis or encephalopathy/coma)	Discontinue everolimus
Recurrence of intolerable grade 2 mucositis or grade 3 event after dose reduction	Reduce dose to the next lower dose level, if available. The lowest possible dose level of everolimus is 2.5 mg daily. Below this level, everolimus must be discontinued.
Recurrence of grade 4 after dose reduction	Discontinue everolimus
Any non-hematologic toxicity requiring Everolimus interruption for $>$ 28 days	Discontinue everolimus

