Premature patient withdrawal	Point/time when the patient exits from the study prior to the planned completion of all study treatment administration and/or assessments; at this time all study treatment administration is discontinued and no further assessments are planned, unless the patient will be followed for progression and/or survival
Stop study participation	Point/time at which the patient came in for a final evaluation visit or when study treatment was discontinued whichever is later
Study treatment	Includes any drug or combination of drugs in any study arm administered to the patient (subject) as part of the required study procedures, including placebo and active drug run-ins.  In specific examples, it is important to judge investigational treatment component relationship relative to a study treatment combination; study treatment in this case refers to the investigational and non-investigational treatments in combination.
Study treatment discontinuation	Point/time when patient permanently stops taking study treatment for any reason; may or may not also be the point/time of premature patient withdrawal
Supportive treatment	Refers to any treatment required by the exposure to a study treatment, e.g. premedication of vitamin supplementation and corticosteroid for pemetrexed disodium.
Variable	Identifier used in the data analysis; derived directly or indirectly from data collected using specified assessments at specified time points

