**Table 6-6 Management of non-infectious pneumonitis**

Worst grade pneumonitis	Suggested investigations	Management of pneumonitis	Everolimus dose adjustment
Grade 1	CT scans with lung windows.	No specific therapy is required	No dose adjustment required. Initiate appropriate monitoring.
Grade 2	CT scan with lung windows. Consider pulmonary function testing includes: spirometry, DLCO, and room air O 2 saturation at rest. Consider a bronchoscopy with biopsy and/or BAL. Monitoring at each visit until return to ≤ grade 1. Return to initial monitoring frequency if no recurrence.	Symptomatic only. Consider corticosteroids and/or other supportive therapy if symptoms are troublesome.	Rule out infection and consider interruption of everolimus until symptoms improve to Grade ≤ 1. Re-initiate everolimus at one dose level lower. Discontinue everolimus if failure to recover within ≤ 28 days.
Grade 3	CT scan with lung windows and pulmonary function testing includes: spirometry, DLCO, and room air O 2 saturation at rest. Monitoring at each visit until return to ≤ grade 1. Return to initial monitoring frequency if no recurrence. Bronchoscopy with biopsy and/or BAL is recommended.	Consider corticosteroids if infective origin is ruled out. Taper as medically indicated.	Rule out infection and interrupt everolimus until symptoms improve to Grade ≤ 1. Consider re-initiating everolimus at one dose level lower (approximately 50% lower than the dose previously administered depending on individual clinical circumstances) Discontinue everolimus if failure to recover within ≤ 28 days.
Grade 4	CT scan with lung windows and required pulmonary function testing, if possible, includes: spirometry, DLCO, and room air O 2 saturation at rest. Monitoring at each visit until return to ≤ grade 1. Return to initial monitoring frequency if no recurrence. Bronchoscopy with biopsy and/or BAL is recommended if possible.	Consider corticosteroids if infective origin is ruled out. Taper as medically indicated.	Rule out infection and discontinue everolimus.

For patients receiving both everolimus and temozolomide: if everolimus is stopped due to toxicity, patients may continue to be treated with temozolomide at the discretion of the treating investigator.

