### 7.1.3 Follow-up Assessments

- Protocol Completion Assessment:

- After administration of everolimus for two years, patients will have completed study treatment.
- All patients must be observed for safety for 30 days following the last dose of everolimus prior to withdrawal from study. This defines completion of active study participation.
- Physical examination and comprehensive neurologic examination and grading, vital signs including weight, Karnofsky Performance status, all laboratory values, and MRI of the brain must be repeated within 4 weeks of the last day of study only if these have not been evaluated within 14 days, inclusive, prior to the date of withdrawal from study, if patients are able to return to do so. If patients are unable to return for an in-person visit, then they will be contacted by phone to assess toxicity at approximately 4 weeks after that last day of study.
- Quality of Life Surveys (optional): 2 surveys will be completed 1 year post-completion of treatment or at the time of tumor progression if sooner than 1 year post-completion of treatment.
- Long-term Follow-up:
  - After completion of study treatment, patients whose tumors have not progressed will be followed with interval MRIs. These should be done every 4 months (+/- 2 weeks) for 1 year, then every 6 months (+/- 4 weeks) for an additional 2 years, and thereafter as per the discretion of the managing physician.
  - Patients will be followed according to routine clinical practice after removal from protocol therapy or until death, whichever occurs first.
  - Patients removed from protocol therapy for unacceptable adverse events will be followed until resolution or stabilization of the adverse event.
  - Patients off protocol therapy will continue to be followed for PFS and OS only for the purposes of this protocol. If patients are not being seen regularly in clinic, then phone calls for PFS and OS will be made every 6 months.

**Table 7-1** Visit evaluation schedule (note: 1 cycle = 28 days)

Procedures:	Initial Screen	1-month Assessment (by phone)	Assessments every 2 cycles (+/- 7 days unless otherwise noted) for cycles 1-12 of therapy	Assessments every 3 cycles (+/- 7 days unless otherwise noted) for cycles 13-24 of therapy	28 days after completing protocol therapy (+/- 7 days) †	Long Term Follow-Up
Clinical Evaluation: ‡						
Medical History	X					
Vital Signs and KPS ¥	X		X	X	X	
Physical Exam, Neurologic Exam	X		X	X	X	

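### Two rows of Table 6-2 conflict on intolerable grade 2 mucositis or a grade 3 event unresolved at 28 days, so whether an Arm 2 patient may continue temozolomide depends on the row read

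*Combined protocol and SAP*

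**What the plan says.** Table 6-2 (Section 6.2.2) has a row for "Intolerable grade 2 mucositis, or grade 3 AE, except hyperglycemia or hypertriglyceridemia or hypercholesterolemia". Everolimus is held until recovery, and the row ends: "Patients will be withdrawn from the study if they fail to recover to" grade 1 or less, or baseline, within 28 days.

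The last row of the same table covers "Any non-hematologic toxicity requiring Everolimus interruption for" more than 28 days. Its action is to discontinue everolimus; withdrawal from the study is not mentioned. The row for any other grade 4 event has no withdrawal sentence either.

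The glossary treats stopping study treatment and premature withdrawal as separate events that need not coincide. Of premature withdrawal it says: "at this time all study treatment administration is discontinued and no further assessments are planned, unless the patient will be followed for progression and/or survival".

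For Arm 2, the paragraph after Table 6-6 (Section 6.2.2.6) says: "if everolimus is stopped due to toxicity, patients may continue to be treated with temozolomide at the discretion of the treating investigator".

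On follow-up, Section 7.1.3 says: "Patients off protocol therapy will continue to be followed for PFS and OS only for the purposes of this protocol". Section 9.1 counts progression after study drug has stopped and censors event-free patients at last contact. Section 9.5 specifies analysis by intention to treat.

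**The concern.** One clinical course has two written outcomes. In Arm 2 the outcomes differ in treatment: one ends temozolomide along with everolimus, the other leaves it to the investigator. Temozolomide is half of the regimen that Arm 2 is meant to test, so its delivery should not turn on which line of a table is consulted.

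There is a second, smaller exposure. The withdrawal row does not say whether the patient stays in PFS and OS follow-up. Someone who takes the words at face value could stop imaging and contact. The patient would then be censored at last contact, and analysing by intention to treat does not recover outcomes that were never collected.

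**Working it through.** The point rests on comparing text. The plan gives no figure for it. The nearest design figure, the 86% in Section 9.3, reproduces: with 35 patients, 50% against 70%, and a rule of at least 22 of 35, the exact binomial gives a one-sided error of 0.088 and power of 0.865. It does not depend on either row.

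1. **Do the rows overlap?** Everolimus is held until recovery. An event in the first row that is still unrecovered after 28 days is therefore also a non-hematologic toxicity with an interruption of more than 28 days. It meets both rows, and nothing says which governs.

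2. **How wide is the overlap?** It is limited to intolerable grade 2 mucositis and grade 3 events. The listed metabolic events are excepted. AST/ALT elevation has its own rows in Table 6-2, pneumonitis has Table 6-6, and hematologic toxicity has Table 6-3. Where these set a 28-day limit, they stop everolimus only. Table 6-4 also covers oral mucositis but sets no 28-day limit, so it does not settle the matter.

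3. **Is the order by severity consistent?** No. As written, an unresolved grade 3 event leads to study withdrawal in one row, while an unresolved event in the row for other grade 4 toxicity leads only to stopping everolimus, through the last row.

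4. **What follows in Arm 2?** Withdrawal row plus glossary: all study treatment ends. Last row plus Section 6.2.2.6: temozolomide may continue. Section 6.2.3 does not remove the difference. It requires drug-associated non-hematologic toxicity to be at grade 2 or less, or at baseline, before the next temozolomide course. Table 6-2 requires grade 1 or baseline. A grade 3 event that has fallen only to grade 2 by day 28 can satisfy the first test and fails the second.

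5. **How many cycles for one patient?** Section 4 stops temozolomide after 12 cycles, and Section 7.1.2 fixes cycles at 28 days. A toxicity that starts in cycle 1 passes the 28-day limit in cycle 2. Cycles 3 to 12 are then at stake: 12 − 2 = 10, or 11 if the cycle 2 course was still pending. This is a ceiling for one patient, not an expected loss.

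6. **Does the plan direct that follow-up ends?** No. The glossary excepts patients followed for progression or survival, and Section 7.1.3 says that patients off protocol therapy are so followed, with six-monthly calls if they are not seen in clinic. Section 7.1.3 also uses study withdrawal to mark the end of active participation, after 30 days of safety observation and ahead of long-term follow-up. What is missing is a link from Table 6-2 to that section.

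**The case against.** The case for leaving the text alone has four parts.

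- **Follow-up is protected.** The glossary exception, Section 7.1.3, the PFS definition in Section 9.1 and the intention-to-treat statement in Section 9.5 all point one way. This stands.
- **Arms 1 and 3 are not in real conflict.** One can stop everolimus, end active participation and continue PFS and OS follow-up without breaking either row. This also stands, so the treatment conflict is confined to Arm 2.
- **Continuing temozolomide is only an option, and Section 6.2.3 would hold it anyway.** This stands for a patient still at grade 3 on day 28, who could not be dosed that day on either reading. It fails for a patient who has improved to grade 2. An option that one row allows and another removes is still a contradiction.
- **There are no other participating sites, and cases are discussed monthly** (Appendix 3). This limits inconsistency but supplies no rule.

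A reader might infer more: that the withdrawal row biases PFS-33 or PFS-38 upward. Suppose a share w of patients is withdrawn with no further follow-up, patients remaining have 70% PFS-33, and withdrawn patients would have had q. Kaplan-Meier then tends to 70%, while the intention-to-treat value is (1 − w) × 70% + w × q. With w = 5% and q = 50% this is 66.5 + 2.5 = 69.0%, a bias of 1 point. With w = 20% and q = 40% it is 56 + 8 = 64.0%, a bias of 6 points. With q = 70% there is none.

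The documents do not support that reading. They give neither w nor q, and the calculation needs a complete loss of follow-up that the plan does not direct. A 20% share from this row alone is also extreme, since Section 9.4 suspends accrual if more than 20% stop drug for toxicity of any kind.

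**Conclusion.** The contradiction is real and narrow. It covers intolerable grade 2 mucositis and grade 3 events outside the exceptions and the dedicated rows and tables, when recovery to grade 1 or baseline has not occurred within 28 days. Its firm consequence is in Arm 2, where the row read decides whether temozolomide may continue, for up to 10 or 11 cycles in a single patient. That rests on reading withdrawal as the glossary defines it.

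Loss of PFS follow-up is a residual risk from a missing cross-reference. It is not something the plan instructs, and a threat to the primary endpoint has not been shown. If Section 7.1.3 is followed, this row causes no bias. If it is not, the size cannot be derived from the documents. The wording should be corrected because the Arm 2 rule is undecided and the change is cheap.

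**What to change.** Reconcile the two rows of Table 6-2 with each other, with the glossary entry on premature withdrawal and with the temozolomide paragraph after Table 6-6, so that one consequence applies and its meaning for Arm 2 is explicit. The same edit should settle whether the difference between the grade 3 and grade 4 rows is intended. Which treatment rule is right is for the investigators; this review takes no view.

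Separately, add a cross-reference from Table 6-2 to Section 7.1.3 stating that stopping treatment, or ending active participation, because of toxicity does not end PFS and OS follow-up.

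The cost is a wording amendment. It adds no visits or procedures, because the follow-up is already planned in Section 7.1.3.
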